#### 13.1.1. AEs of Special Interest

See Section [9.1.3](#) for management of anticipated adverse events.

#### 13.1.2. Reporting of AEs

Any AE occurrence (spontaneously volunteered and enquired for, as well as observed AEs) during the study must be documented in the patient's medical records in accordance with the Investigator's normal clinical practice and on the

AE page of the eCRF. SAEs that occur during the study must be documented in the patient's medical record, on the AE eCRF, and on the SAE form.

The Investigator should attempt to establish a diagnosis of the event based on the signs, symptoms, and/or other clinical information. In such cases, the diagnosis should be documented as the AE (and SAE if serious) and not the individual signs/symptoms.

If an abnormal laboratory finding or other abnormal assessment meets the definition of an AE, then the AE eCRF page must be completed as appropriate. In addition, if the abnormal assessment meets the criteria for being serious, the SAE form must also be completed. A diagnosis, if known, or clinical signs or symptoms if the diagnosis is unknown, rather than the clinically significant laboratory finding or abnormal assessment, should be used to complete the AE/SAE page. If no diagnosis is known and clinical signs or symptoms are not present, then the abnormal finding should be recorded. If an SAE report is completed, pertinent laboratory data should be recorded on the SAE form, preferably with baseline values and copies of laboratory reports.

A database of all adverse events (not just those considered related to the study drug) will be maintained in a 21 CFR Part 11 compliant database. The event will be categorized by organ system, relationship to treatment, its grade of severity, and resolution. The PI and study statistician will periodically review the collective adverse events with the intention of identifying any trends or patterns in toxicity. If any such trends are identified, depending on their severity and frequency, a protocol amendment will be considered.

### **13.2. Serious Adverse Events**

An AE is considered "serious" if in the opinion of the investigator it is one of the following outcomes:

- Fatal
- Life-threatening
- Constitutes a congenital anomaly or birth defect
- A medically significant condition (defined as an event that compromises subject safety or may require medical or surgical intervention to prevent one of the three outcomes above).
- Requires inpatient hospitalization or prolongation of existing hospitalization
- Results in persistent or significant incapacity or substantial disruption to conduct normal life functions.
- Suspected transmission of an infectious agent (eg, pathogenic or nonpathogenic) via the study drug is an SAE.

Note: Although pregnancy, overdose, potential drug-induced liver injury (DILI), and cancer are not always serious by regulatory definition, these events must be handled as SAEs.

### **13.2.1. Reporting of SAEs**

Following the subject's written consent to participate in the study, all SAEs, whether related or not related to study drug, should be collected, including those thought to be associated with protocol-specified procedures. The investigator should report any SAE occurring after these aforementioned time periods, which is believed to be related to study drug or protocol-specified procedure.

All SAEs should be reported immediately to the Principal Investigator or designee. Only adverse events that the Principal Investigator determines to be serious, unanticipated, and related or possibly/probably (i.e. more likely than not) related to the research must be reported to the Duke IRB. An SAE report should be completed for any event where doubt exists regarding its seriousness. If the investigator believes that an SAE is not related to study drug, but is potentially related to the conditions of the study (such as withdrawal of previous therapy or a complication of a study procedure), the relationship should be specified in the narrative section of the SAE Report Form. Reportable adverse events will be submitted in the electronic IRB system, according the following guidelines:

- Report within 24 hours of learning about any subject's death that was unanticipated and more likely related to the research than unrelated;
- Report within 5 business days of learning about any serious AE that is unanticipated and related or possibly/probably related to study treatment;
- Report within 10 business day of learning about any other unanticipated problem or event that was more likely related to the study treatment than unrelated.

The PI-Sponsor must report to the FDA, in an IND safety report, any suspected adverse reaction that is both serious and unexpected. Before submitting this report, the PI-Sponsor needs to ensure that the event meets all three of the definitions contained in the requirement:

- Suspected adverse reaction (i.e. there is a reasonable possibility that the drug caused the adverse event)
- Serious
- Unexpected (see nivolumab and/or ipilimumab investigator brochures)

If the adverse event does not meet all three of the definitions, it should not be submitted as an expedited IND safety report. The PI-Sponsor is required to report to the FDA all IND Safety reports in writing within 15 days (7 days for unexpected fatal or life-threatening suspected adverse reaction). The FDA Form 3500A can be found on the FDA website, [www.fda.gov](http://www.fda.gov). All other adverse events will be reported to the FDA in the Annual Report.

All Serious Adverse Events (SAEs) that occur following the subject's written consent to participate in the study through 100 days of discontinuation of dosing must be reported to BMS Worldwide Safety, whether related or not related to study drug. SAEs must be collected that relate to any later protocol-specified procedure (eg, surgery and SRS). SAEs, whether related or not related to study drug, and pregnancies (including in a female partner of a male participant) must be reported to BMS within 24 hours \ 1 Business Day of becoming aware of the event. Pregnancies must be reported and submitted to BMS on any of the following form(s):

1. MedWatch or, CIOMS or
2. BMS Pregnancy Surveillance Form or,
3. Approved site SAE form

SAEs should be reported to BMS using a Medwatch form, must include the BMS protocol number, and should be either emailed or faxed as below.

**SAE Email Address:** [contact]

**SAE [contact]

If only limited information is initially available, follow-up reports are required. (Note: Follow-up SAE reports should include the same investigator term(s) initially reported.)

If an ongoing SAE changes in its intensity or relationship to study drug or if new information becomes available, a follow-up SAE report should be sent within 24 hours \ 1 Business Day to BMS using the same procedure used for transmitting the initial SAE report.

All SAEs should be followed to resolution or stabilization.

### **13.3. Emergency Unblinding of Investigational Treatment**

Not applicable.

### **13.4. Other Reportable Information**

Not applicable.

### **13.5. Special Warnings and Precautions**

Not applicable.

### **13.6. Safety Oversight Committee (SOC)**

The Duke Cancer Institute SOC is responsible for annual data and safety monitoring of DUHS sponsor-investigator phase I and II, therapeutic interventional studies that do not have an independent Data Safety Monitoring Board (DSMB). The primary focus of the SOC is review of safety data, toxicities and new information that may affect subject safety or efficacy. Annual safety reviews includes but may not be limited to review of safety data, enrollment status, stopping rules if applicable,

accrual, toxicities, reference literature, and interim analyses as provided by the sponsor-investigator. The SOC in concert with the DCI Monitoring Team (see Section 14.1 for Monitoring Team description) oversees the conduct of DUHS cancer-related, sponsor-investigator greater-than-minimal-risk intervention studies that do not have an external monitoring plan, ensuring subject safety and that the protocol is conducted, recorded and reported in accordance with the protocol, standing operating procedures (SOPs), Good Clinical Practice (GCP), and applicable regulatory requirements.

## 14. QUALITY CONTROL AND QUALITY ASSURANCE

### 14.1. Monitoring

This clinical research study will be monitored both internally by the PI, and institutionally by the Duke Cancer Institute (DCI). In terms of internal review the PI will continuously monitor and tabulate adverse events. Appropriate reporting to the Duke University Medical Center IRB will be made. If an unexpected frequency of Grade III or IV events occur, depending on their nature, action appropriate to the nature and frequency of these adverse events will be taken. This may require a protocol amendment, dose de-escalation, or potentially closure of the study. The PI of this study will also continuously monitor the conduct, data, and safety of this study to ensure that:

- Interim analyses occur as scheduled;
- Stopping rules for toxicity and/or response are met;
- Risk/benefit ratio is not altered to the detriment of the subjects;
- Appropriate internal monitoring of AEs and outcomes is done;
- Over-accrual does not occur;
- Under-accrual is addressed with appropriate amendments or actions;
- Data are being appropriately collected in a reasonably timely manner.

DCI Protocol Review and Monitoring systems (PRMS) review of this protocol begins with an initial review by the Cancer Protocol Committee (CPC). CPC new protocol review focuses on scientific relevance, study design, adequacy of biostatistical input, protocol prioritization, feasibility of completing the study within a reasonable time frame and risk assessment of the trial. The PI will abide by CPC assessment of the level of risk, which will determine the intensity of subsequent DCI monitoring. CPC also conducts annual scientific progress reviews on protocols that are open to enrollment and focus on protocol prioritization, accrual and scientific progress. These reviews are conducted at the time of IRB annual renewals and documentation of all CPC reviews will be maintained in eIRB/iRIS systems.

A determination for the degree of monitoring conducted by the DCI monitoring team is made at the time of initial CPC approval to commensurate with the type and level of intervention, phase, endpoints, degree of risk, size and complexity of the protocol. A formal, independent monitoring will be conducted by the DCI monitoring team according to the risk level and monitoring plan assigned by the CPC until the study is closed to enrollment or subjects are no longer receiving study drug or other interventions that are more than minimal risk. Additional monitoring may be prompted by findings from monitoring visits, unexpected frequency of serious and/or unexpected toxicities, or other concerns. Monitoring visits may also be initiated upon request by DUHS and DCI Leadership, CPC, SOC, a sponsor, an investigator, or the IRB.

The DCI monitoring team reviews the adequacy of informed consent, enrollment of eligible patients, implementation of protocol-specified procedures and treatment, adequacy of data collection, and appropriateness of adverse event monitoring and

reporting. The DCI monitoring team presents final monitoring reports to the DCI Safety Oversight Committee (SOC) highlighting safety concerns and unresolved issues. The SOC, at a convened meeting, assigns an overall rating of satisfactory, marginal, or unsatisfactory to reflect the overall quality of data, regulatory, consent, eligibility, study conduct and AE reporting. Corrective action plans (CAPs) are developed, implemented, and evaluated as indicated. The SOC will notify the sponsor-investigator and DUHS IRB when significant safety concerns are identified.

The SOC in concert with DCI monitoring team conducts data and safety monitoring for DUHS sponsor-investigator phase I and II, therapeutic interventional oncology studies that do not have an independent DSMB. These reviews occur at a minimum annually and more frequently for the high risk studies. The SOC safety reviews include review of safety data, enrollment status, stopping rules if applicable, accrual, toxicities, reference literature, and interim analyses as provided by the sponsor-investigator. The SOC, at a convened meeting, assigns a rating of satisfactory when adequate accrual with lack of excessive toxicity is present.

## **14.2. Audits**

The Duke Office of Audit, Risk and Compliance (OARC) may conduct confidential audits to evaluate compliance with the protocol and the principles of GCP. The PI agrees to allow the OARC auditor(s) direct access to all relevant documents and to allocate his/her time and the time of the study team to the OARC auditor(s) in order to discuss findings and any relevant issues.

OARC audits are designed to protect the rights and well-being of human research subjects. OARC audits may be routine or directed (for cause). Routine audits are selected based upon risk metrics generally geared towards high subject enrollment, studies with limited oversight or monitoring, Investigator initiated Investigational Drugs or Devices, federally-funded studies, high degree of risk (based upon adverse events, type of study, or vulnerable populations), Phase I studies, or studies that involve Medicare populations. Directed audits occur at the directive of the IRB or an authorized Institutional Official.

OARC audits examine research studies/clinical trials methodology, processes and systems to assess whether the research is conducted according to the protocol approved by the DUHS IRB. The primary purpose of the audit/review is to verify that the standards for safety of human subjects in clinical trials and the quality of data produced by the clinical trial research are met. The audit/review will serve as a quality assurance measure, internal to the institution. Additional goals of such audits are to detect both random and systemic errors occurring during the conduct of clinical research and to emphasize “best practices” in the research/clinical trials environment.

## **14.3. Data Management and Processing**

### **14.3.1. Case Report Forms (CRFs)**

The electronic CRF (eCRF) will be the primary data collection document for the study. The CRFs will be updated in a timely manner following acquisition of new source data. Only the PI, the study coordinator, the data management team, and the clinical trials coordinator are permitted to make entries, changes, or corrections in the eCRF.

An audit trail will be maintained automatically by the electronic CRF management system, Advarra OnCore. Designated personnel will complete user training, as required or appropriate per regulations.

#### **14.3.2. Data Management Procedures and Data Verification**

Access to the electronic databases will be managed by the PRTBTC Data Manager.

Completeness of entered data will be checked by the PRTBTC Data Manager or designee, and users will be alerted to the presence of data inconsistencies. Additionally, the data manager and the statistical team will cross-reference the data to verify accuracy. Missing or implausible data will be highlighted for the PI requiring appropriate responses (i.e. confirmation of data, correction of data, completion or confirmation that data is not available, etc.).

The database will be reviewed and discussed prior to database closure, and will be closed only after resolution of all remaining queries. An audit trail will be kept of all subsequent changes to the data.

#### **14.3.3. Study Closure**

Following completion of the studies, the PI will be responsible for ensuring the following activities:

- Data clarification and/or resolution
- Accounting, reconciliation, and destruction/return of used and unused study drugs
- Review of site study records for completeness
- Shipment of all remaining laboratory samples to the designated laboratories

## 15. STATISTICAL METHODS AND DATA ANALYSIS

All statistical analysis will be performed under the direction of the statistician designated in key personnel. Any data analysis carried out independently by the investigator must be approved by the statistician before publication or presentation.

### 15.1. Study Design Overview

This randomized phase II trial is conducted among patients with surgically-resectable, solid tumor brain metastases to assess the impact of neoadjuvant nivolumab and ipilimumab administered before surgery and stereotactic radiosurgery on various clinical and biological endpoints.

The study was originally designed as a randomized phase 2 trial in which patients were randomized via a permuted block randomization algorithm using a 1:1 allocation ratio to receive either Arm 1 (with neoadjuvant nivolumab and ipilimumab) or Arm 2 (without neoadjuvant treatment). Unfortunately, the study faced challenges to enrollment due to delays in treatment caused by the randomizing of patients to a control arm. In a Memo to File dated March 4, 2021 that was submitted to the IRB and FDA, we proposed the removal of randomization in favor of a single-arm study in which all patients will receive neoadjuvant immunotherapy prior to their resection and SRS. This change is reflected in the protocol's amendment date 03/19/2021. This change will not affect the primary endpoint of feasibility. Prior to the writing of this Memo to File, 1 patient had been randomized to receive standard of care surgery and SRS without neoadjuvant immunotherapy. This patient, though eligible, will not be part of the analyses described below.

### 15.2. Analysis Sets

The primary analysis associated with the assessment of feasibility, survival, progression-free survival, and time to intracranial progression will include all eligible patients who receive both nivolumab and ipilimumab.

Correlative analyses may be limited to only those patients who provide adequate specimens for analyses.

### 15.3. Patient Demographics and Other Baseline Characteristics

Summaries of clinical and socio-demographic characteristics will be generated for all enrolled patients. Categorical descriptors will be summarized using frequency distributions; whereas, interval variables will be summarized using percentiles, as well as means and standard deviations.

### 15.4. Treatments

A CONSORT diagram will be generated that describes flow of treatment. The diagram will provide information about the number of patients who receive

neoadjuvant treatment, undergo surgery (on schedule, late, or not at all), and receive SRS. Details about the SRS administered will be summarized.

The number of patients who receive treatment after SRS will also be tabulated with some detail about the type of treatment administered. Data about maintenance treatment, including the type of immunotherapy, will also be summarized.

## **15.5. Primary Objectives**

This study has two primary objectives. This includes an assessment of the feasibility of administering ipilimumab and nivolumab before surgery and SRS in patients with solid tumor brain metastases, as well as an assessment of the effect of neoadjuvant treatment on the proliferation of circulating T-cells.

### **15.5.1. Primary Objective #1: Feasibility (Surgical Delay)**

#### **15.5.1.1. Variable**

The first primary objective is to demonstrate that neoadjuvant administration of ipilimumab and nivolumab administered to patients with solid tumor brain metastases before surgery and SRS is feasible. Feasibility will be assessed by the proportion of patients who have their surgery delayed or surgery never occurs as a direct or indirect result of ipilimumab and/or nivolumab treatment. With the checkpoint inhibitors being administered on Day -7, the surgery is scheduled for Week 1, Day 1 ( $\pm$  3 days). *Surgery will be considered delayed if it never occurs or occurs after Day 4 (i.e. Day 1 + 3).*

#### **15.5.1.2. Continuous Monitoring of Feasibility and Analysis**

The proportion of patients experiencing surgical delay as defined in Section 15.5.1.1 will be computed as the number of patients with delayed surgery or whom never have surgery as a direct or indirect result of ipilimumab and/or nivolumab treatment divided by the total number of patients.

Neoadjuvant treatment patients who have delayed surgery or no surgery due to reasons unrelated to ipilimumab and/or nivolumab treatment will be excluded from the assessment of feasibility. However, this patient will be included in all other analyses if data is available. Reasons for such exclusions will be tabulated. All other patients will be considered evaluable for the assessment of feasibility.

Methods developed for continuous monitoring of toxicity will assess whether the number of surgical delays is not excessive. Based upon the Pocock boundary, the following monitoring rules were developed assuming that a true surgical delay rate of 10% is acceptable, and a surgical delay rate of 20% is too high. Accrual of patients will be suspended if the following conditions are satisfied:

# of Patients Enrolled to Date	Suspend Treatment Assignment if
1 – 4	# Evaluable Patients with Delayed Surgery > 1
5 – 8	# Evaluable Patients with Delayed Surgery > 2
6 – 14	# Evaluable Patients with Delayed Surgery > 3
15+	# Evaluable Patients with Delayed Surgery > 4

These monitoring rules were generated using the R software package. Specifically, the toxbdry function in the clinfun package (<https://cran.r-project.org/web/packages/clinfun/clinfun.pdf>) that implements methods developed by Jennison and Turnbull [20] and Ivanova et al [21] was used.

If accrual is suspended, the reasons for delay will be carefully reviewed to determine whether accrual should continue without any protocol modification, be permanently terminated, or whether modifications to the treatment regimen (e.g., removal of ipilimumab from the treatment regimen) should occur.

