## 5. PROTOCOL SYNOPSIS AND RESEARCH SUMMARY

### 5.1. Purpose

A phase II study of neoadjuvant nivolumab and ipilimumab in patients with surgically-resectable, solid tumor brain metastases is planned to address the following objectives.

Primary Objectives:

1. Assess the feasibility of neoadjuvant ipilimumab and nivolumab treatment before surgery and SRS in patients with solid tumor brain metastases as measured by the proportion of patients who have their surgery delayed or surgery never occurs.
2. Demonstrate that neoadjuvant immunotherapy will increase proliferation of circulating T-cells compared to baseline measurements.

Exploratory Objectives:

1. Describe the survival of patients with solid tumor brain metastases receiving neoadjuvant ipilimumab and nivolumab followed by surgery and SRS.
2. Describe the time to local intracranial progression.
3. Describe the time to distant intracranial progression.
4. Describe the time to overall intracranial progression.
5. Describe progression-free survival.
6. Quantify the rate of radiation necrosis.
7. Describe the immune expression profile of patients treated with neoadjuvant ipilimumab and nivolumab.

Hypotheses

This is a hypothesis testing protocol designed to test the following hypotheses:

1. Neoadjuvant immunotherapy will not delay surgical resection for patients with solid tumor brain metastases.
2. Neoadjuvant immunotherapy will increase Ki67 on circulating PDL-1+/CD8+ T-cells among patients with solid tumor brain metastases.

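### The primary feasibility proportion counts only delays judged drug-related and deletes treated patients whose late or absent surgery is judged unrelated, so it does not show how often treated patients miss timely surgery and it conflicts with Sections 9.4 and 15.2

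*Combined protocol and SAP*

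**What the plan says.** The combined protocol and SAP defines the first primary endpoint in several ways.

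- **Objective (Section 5.1):** feasibility "as measured by the proportion of patients who have their surgery delayed or surgery never occurs", with no reference to cause. Section 5.6 also describes delay without attribution and divides by all patients.
- **Endpoint table (Section 8) and variable (Section 15.5.1.1):** delay must be linked to the immunotherapy. Section 15.5.1.1 then adds an unattributed rule: "Surgery will be considered delayed if it never occurs or occurs after Day 4".
- **Analysis (Section 15.5.1.2), first paragraph:** the numerator is late or absent surgery "as a direct or indirect result of ipilimumab and/or nivolumab treatment divided by the total number of patients".
- **Analysis (Section 15.5.1.2), second paragraph:** treated patients with late or no surgery "due to reasons unrelated to ipilimumab and/or nivolumab treatment will be excluded from the assessment of feasibility". It continues: "Reasons for such exclusions will be tabulated. All other patients will be considered evaluable for the assessment of feasibility".
- **Section 9.4:** everyone who starts checkpoint treatment is in the feasibility denominator, operated on or not.
- **Section 15.2:** the feasibility analysis includes all eligible patients given both drugs.

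The suspension rule counts delays among evaluable patients, "assuming that a true surgical delay rate of 10% is acceptable, and a surgical delay rate of 20% is too high". The trial is unblinded (Section 9.1.6) and its control arm has been removed (Sections 9.1.7 and 15.1). On that removal, Section 15.1 says: "This change will not affect the primary endpoint of feasibility".

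**The concern.** A patient operated on in time can never be excluded. A patient whose operation is late or cancelled can be, by a judgement made after the event is known. The plan gives no criteria for that judgement, names no adjudicator and provides no all-cause companion figure.

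The judgement is also difficult in this setting. Section 9.1.3 notes that peritumoral inflammation may come from the disease itself or from immune infiltration of the brain. The same pre-operative decline could reasonably be assigned to either. That choice decides whether the patient is an event or disappears from the assessment. With no concurrent untreated group, there is no background delay rate against which to check the labels.

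At stake are the first primary endpoint and the only numeric suspension rule in the plan. As written, the analysis estimates drug-attributed delay among patients with no other cause of delay. It does not estimate how often a treated patient fails to reach surgery on time, which is what the Section 5.1 objective asks.

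**Working it through.** **Inputs from the plan.** Acceptable rate 10%, too-high rate 20%, and suspension at more than 1, 2, 3 or 4 delays as enrolment grows (Section 15.5.1.2). Up to 20 treated patients (Sections 5.3 and 9.1).

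**Assumed.** The share f of delays called unrelated is not given, so it is varied over 25%, 50% and 75%. Patients are taken as independent with a constant rate.

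**Step 1: reproduce the boundary.** "Based upon the Pocock boundary, the following monitoring rules were developed". Take the smallest count r with P(X ≥ r | n, 0.10) ≤ c. With c = 0.0525 this gives r = 2 for n = 1–4, 3 for 5–8, 4 for 9–14 and 5 for 15–20. The binding values are P(X ≥ 2 | n = 4) = 0.0523, just inside, and P(X ≥ 3 | n = 9) = 0.0530, just outside. This matches the stated limits if the third row, printed as 6–14 and overlapping the second, is read as 9–14. Exact recursion over 20 patients gives a suspension probability of 10.4% at a counted rate of 10% and 47.2% at 20%. If the third row applies from n = 6, these are 9.6% and 45.9%.

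**Step 2: separate attribution from deletion.** Let t be the all-cause rate of late or absent surgery.

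- Attributed numerator, everyone kept: t(1 − f).
- Attributed numerator, unrelated delays deleted (the plan): t(1 − f) / (1 − tf).

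With t = 0.20:

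| f | Everyone kept | Deleted (plan) | P(suspend by 20) |
|---|---|---|---|
| 0 | 20.0% | 20.0% | 47.2% |
| 0.25 | 0.15 = 15.0% | 0.15/0.95 = 15.8% | 26.6% |
| 0.50 | 0.10 = 10.0% | 0.10/0.90 = 11.1% | 10.4% |
| 0.75 | 0.05 = 5.0% | 0.05/0.85 = 5.9% | 2.0% |

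At f = 0.50, attribution lowers the figure by 10 points (20% to 10%) and deletion raises it by 1.1 points (10% to 11.1%). The suspension column counts drug-attributed delays with rows chosen by number enrolled, as the table is labelled. Choosing rows by number evaluable gives 28.1%, 12.3% and 2.8%. Starting the third row at n = 6, again by number enrolled, gives 25.4%, 9.6% and 1.8%.

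**Step 3: a higher all-cause rate.** At t = 0.30, the expected reported proportions are 24.3%, 17.6% and 9.7%. Suspension probabilities are 57.3%, 26.6% and 5.2%, against 81.6% if every delay counted.

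**Step 4: one concrete data set.** Take 20 treated patients with 2 related and 2 unrelated delays.

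- Section 15.5.1.2 with the exclusion: 2/18 = 11.1% (exact 95% CI 1.4% to 34.7%).
- Drug-attributed over all treated: 2/20 = 10%.
- All-cause over all treated: 4/20 = 20.0% (5.7% to 43.7%).

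The documents support each of these calculations somewhere, and the plan does not say which one prevails.

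**The case against.** Drug-attributed delay is a legitimate and deliberate endpoint. Sections 8, 15.5.1.1, 15.5.1.2 and 15.5.1.3 all use it, and the first hypothesis in Section 5.1 asks whether immunotherapy delays resection. A cancelled operating slot says nothing about the drugs. The plan also has safeguards: indirect effects count, exclusion reasons are tabulated, the CONSORT diagram in Section 15.4 shows surgery on schedule, late or absent, and suspension leads to a review rather than closure. All of this stands. An all-cause figure could be recovered descriptively afterwards, but the primary proportion and the suspension count would not change.

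A reader might go further and infer that deleting patients is what pulls the rate down and weakens the suspension rule. The documents do not support that. Under the attributed endpoint, deletion slightly raises the proportion (11.1% against 10%). It does not lower the suspension count either, because a delay judged unrelated would not be counted even if the patient were kept. The downward shift comes from the attributed numerator.

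A reader might also infer that the plan lets a rate it calls too high pass as acceptable. That sets an all-cause 20% against benchmarks that Section 15.5.1.2 applies to delay as defined in Section 15.5.1.1, which is most naturally read as drug-attributed. If half of a 20% all-cause rate is correctly labelled unrelated, the attributed rate really is 10%, and a 10.4% chance of suspension is the rule working as intended.

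**Conclusion.** The concern holds in this form. The primary feasibility proportion rests on an unblinded attribution with no stated criteria and no control arm, and it deletes only patients who already have the outcome. This contradicts Section 9.4, Section 15.2, the denominator in the first paragraph of Section 15.5.1.2 and the unattributed objective in Sections 5.1 and 5.6. Section 15.1 may be right that the endpoint's definition did not change when the control arm was dropped, but no concurrent delay rate is now available to test the labels.

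The result understates failure only relative to all-cause failure of the strategy, or where delays are wrongly called unrelated. Over the assumed unrelated shares of 25% to 75%, a 20% all-cause rate appears as 15.8% down to 5.9%, and the suspension probability falls from 47.2% to between 26.6% and 2.0%. How much of that is a real loss depends on two things the documents do not settle: how accurate the labels will be, and whether 10% and 20% were meant as all-cause rates. The inconsistency over who is in the denominator does not depend on these assumptions.

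**What to change.** 1. Remove the exclusion from Section 15.5.1.2 and reconcile it with Sections 9.4 and 15.2, keeping every patient who received both drugs in the feasibility denominator.
2. Report two proportions side by side in that set: all-cause (surgery after Day 4 or never) with an exact 95% CI, and drug-attributed, with unrelated delays kept in the denominator as non-events. Base the feasibility conclusion on both.
3. State in advance what counts as unrelated. State whether the 10% and 20% benchmarks refer to all-cause or drug-attributed delay, and make the suspension count use the same definition.

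The cost is revised wording and one extra table, from surgery dates and delay reasons the plan already needs. The all-cause rate may look less favourable. If the suspension count becomes all-cause, accrual may pause for review more often.
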